8. STATISTICAL METHODS AND ANALYSIS

8.1. Sample Size Calculation

The primary objective of the trial is to assess the safety and tolerability of ⁶⁸Ga-PSMA-R2. Data for this objective will be reported descriptively. No formal statistical sample size calculation was done. The planned sample size includes a total of up to 30 patients which is believed to provide sufficient data to assess the safety and tolerability of ⁶⁸Ga-PSMA-R2, and to reliably estimate distribution and dosimetry parameters. In addition, an overall sample size of 30 patients should provide reasonable precision around estimations of preliminary targeting properties of the ⁶⁸Ga-PSMA-R2 imaging. For example, if patient level agreement of 83.3% if observed (for e.g. if 25 patients had lesions detected by ⁶⁸Ga-PSMA-R2 imaging out of 30 patients in the trial), then the 95% CI around this would be 66.4% to 92.7%.

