3. STUDY DESIGN AND PATIENT POPULATION

3.1. Study Design

This is an open label, multi-center, single dose, Phase 1/2 study to evaluate the safety and tolerability of 3 MBq/Kg, but not less than 150 and no more than 250 MBq, of ⁶⁸Ga-PSMA-R2 in adult patients with PCa expressing PSMA receptors.

This study will consist of 2 phases.

Phase 1:

During the Phase 1 portion of the study, approximately 6 patients with biochemically recurrent PCa will receive the IP and will remain at the site for approximately 6 hours post-injection in order to assess PK, biodistribution, and dosimetry for critical organs. Patients will receive a single dose of 3 MBq/kg, (\geq 150 MBq and \leq 250 MBq), of ⁶⁸Ga-PSMA-R2. The product will be prepared prior to administration and injected intravenously and each patient will undergo a whole-body PET/CT scan following IP administration. Serial blood and urine samples will be collected for PK characterization and dosimetry. Safety assessments will be conducted after IP administration on Day 1, and during follow-up on Days 7 and 28.

Dosimetry will be assessed in 6 patients, they will undergo static whole-body PET/CT images at 0-4 hours to determine absorbed doses by the normal organs and target tumor lesions.

Phase 2:

Two groups of approximately 12 patients will be enrolled in the Phase 2 portion of the study (patients with PCa-BR, and mPCa). Enrollment will be capped at 12 patients in each group to ensure an even distribution of patient condition. If preliminary data analysis from the Phase 1 portion of the study provides sufficient dosimetry data, all patients will undergo whole body PET/CT imaging optimized for time according to the data analysis from the Phase 1 component of the study.

Patients who have signed the informed consent and are eligible for study participation according to the inclusion and exclusion criteria will receive a single intravenous bolus of ⁶⁸Ga-PSMA-R2 on Day 1.

This study is comprised of 4 clinical visits and will be conducted in 3 study periods including: Screening, administration/ imaging, and safety follow-up period (final/early termination).

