4.2. BIODISTRIBUTION, DOSIMETRY AND IMAGING ANALYSIS

The biodistribution, dosimetry and imaging analysis will be split in two:

- The analysis using data from the principal scientist from a third-party radiation dosimetry vendor will be performed only for Phase I.
- The analysis using data from a third-party medical imaging vendor will be performed for both Phase I and

Document:	K:\AAA\Ga-PSMA-R2\VYA27826\ Biostatistics\Documentation\SAP\2.0\Ga-PSMA-R2-SAP_v2.0
Author:	[REDACTED] Version Number: 2.0

Version Date: 29JUN2020

Template No.: CS_TP_BS016 Revision 5
Effective Date: 01Apr2018

Reference: CS_WI_BS005

Phase II.

Summary tables, listings and figures needed for the biodistribution, dosimetry and imaging are described in section 15.

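### Protocol 8.1 rests reliable dosimetry estimates on up to 30 patients, but dosimetry is done in about 6 and no precision is given for that number

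*Protocol*

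**What the plan says.** Protocol 8.1 states that "No formal statistical sample size calculation was done". It continues: "The planned sample size includes a total of up to 30 patients which is believed to provide sufficient data" for safety and tolerability and "to reliably estimate distribution and dosimetry parameters". It then gives one worked example, for patient-level agreement: 25 of 30 patients, 83.3%, with a 95% interval of 66.4% to 92.7%.

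Other sections set the number of patients with dosimetry:

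- Protocol 3.1, Phase 1: "Dosimetry will be assessed in 6 patients". These are patients with biochemically recurrent disease.
- Protocol Table 1, footnotes f to h: four PET/CT time points in Phase 1 and up to two in Phase 2; blood and urine for PK and dosimetry in Phase 1 only.
- Protocol 6.10: patients who discontinue are not replaced.
- Protocol 8.2.2: dosimetry is analysed in the part of the full analysis set that had dosimetry assessments.
- SAP 4.2: the analysis of the radiation dosimetry vendor's data "will be performed only for Phase I". SAP 15 says the same of reporting.

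The synopsis credits the 30 patients with safety and tolerability only and does not mention dosimetry in its sample size entry.

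**The concern.** The subject of the sentence in 8.1 is the total of 30, but the data for one of the aims it names come from about one fifth of that number. Time-activity curves, residence times, absorbed doses and effective dose are all listed secondary endpoints (Protocol 2.2.2). The sample size section is where a reader looks for how firmly such estimates will be known, and it points to the wrong denominator.

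The 30 also span biochemical recurrence and metastatic disease, whereas the Phase 1 set contains no metastatic patients. The mismatch is therefore in population as well as in number. What is at stake is how the dosimetry estimates are read; the safety conclusion is not involved.

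**Working it through.** **1. The plan's own figure.** Inputs from Protocol 8.1: 25 of 30, 95% interval 66.4% to 92.7%. Wilson score interval with p = 25/30 = 0.8333, n = 30, z = 1.96:

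- centre = (p + z²/2n) / (1 + z²/n) = (0.8333 + 0.0640) / 1.1281 = 0.7955
- half-width = z·√(p(1−p)/n + z²/4n²) / (1 + z²/n) = 1.96 × √(0.004630 + 0.001067) / 1.1281 = 0.1311
- interval = 66.4% to 92.7%

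This matches the stated interval. It concerns agreement, not dosimetry. No dosimetry precision is stated, so there is none to reproduce.

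**2. Precision of a mean dosimetry parameter.** Inputs: n = 6 (Protocol 3.1) and, for comparison, n = 30 (Protocol 8.1). Half-width of the 95% t interval = t(0.975, n−1) × SD / √n.

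- n = 6: 2.571 / √6 = 1.05 SD
- n = 30: 2.045 / √30 = 0.37 SD
- ratio: 1.049 / 0.373 = 2.8

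The ratio compares 6 with 30 patients. It does not compare anything with a dosimetry figure in the plan.

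**3. In relative terms.** Neither document gives a between-patient coefficient of variation (CV), so the CVs below are assumptions. Half-width as a percentage of the mean = CV × t / √n:

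| Assumed CV | n = 6 | n = 30 |
|---|---|---|
| 20% | 21.0% | 7.5% |
| 30% | 31.5% | 11.2% |
| 40% | 42.0% | 14.9% |
| 50% | 52.5% | 18.7% |
| 60% | 63.0% | 22.4% |

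**4. The SD itself.** From 6 patients, the 95% interval for the SD runs from √(5/χ²(0.975, 5)) = 0.62 to √(5/χ²(0.025, 5)) = 2.45 times the estimate. The study will therefore say little about between-patient variability.

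**5. Loss of one patient.** With no replacement, n could be 5: 2.776 / √5 = 1.24 SD, which is 37% of the mean at a CV of 30% and 62% at 50%.

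**The case against.** The best defence is that nobody who reads the whole protocol would be misled. Section 3.1, the schedule footnotes, section 8.2.2 and SAP 4.2 and 15 all confine dosimetry to the Phase 1 patients, the PK analysis plan names 6 patients, and the output conventions in SAP Appendix 1 show n. The 30 include the 6, so the sentence can be read loosely as the whole design serving all the aims. Section 8.1 admits that no formal calculation was done. Protocol 8.2 already allows confidence intervals where appropriate, and the planned n, mean and SD let a reader derive one.

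Much of this stands, and it limits the finding to the sample size statement. It does not rescue the sentence: 8.1 never mentions 6, and its next sentence again argues from 30.

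Three stronger readings are tempting but unsupported:

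- *A stated dosimetry precision is false.* Section 8.1 states none; it uses only the word reliably. For the same reason, the factor of 2.8 cannot be called the gap between the text and the truth.
- *The section's arithmetic is wrong.* Its one interval is correct by the Wilson method and refers to all 30 patients.
- *Imprecise dose estimates would set the Phase 2 scan times.* Protocol 6.5.4.1 identifies time points from lesion counts, SUV and tumor-to-background ratios. Section 3.1 makes the reduced imaging conditional on sufficient dosimetry data, but dose values do not choose the times. That condition leaves further dosimetry in Phase 2 not strictly excluded, yet section 6.5.4.3 treats it as met and the SAP plans no such analysis.

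**Conclusion.** The sentence is wrong as written: it rests distribution and dosimetry on a sample size that the design does not deliver for them. The number is about 6, all with biochemical recurrence, and it may be lower if a patient drops out. The expected 95% half-width for a mean is about 1.05 SD, against 0.37 SD had all 30 contributed.

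The SD multiples assume roughly normal, independent patient values. The percentages rest also on the assumed CVs and are illustrative only. The analysis sets are defined consistently elsewhere. The correction is worth making because it is specific and nearly free.

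**What to change.** **Protocol 8.1.** Limit the 30-patient statement to safety and tolerability and to the preliminary targeting properties. Add that PK, biodistribution and dosimetry rest on about 6 Phase 1 patients with biochemical recurrence, without replacement. Section 8.1 does not name PK, but the same patients supply it. Drop the word reliably. Give the expected 95% half-width for a mean as about 1.05 SD. If percentages are wanted, give the range of 21% to 63% of the mean for CVs of 20% to 60% and label the CVs as assumptions, not as expected values. Leave the agreement example unchanged.

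**SAP 15.1.** Report n and a 95% confidence interval with each mean absorbed dose and the mean effective dose, in line with the general provision in Protocol 8.2.

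**Cost.** Wording changes in two documents, a few more table columns, and a less favourable statement of precision. No extra patients, visits or procedures.

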8.2.3. Preliminary Targeting Properties of ⁶⁸Ga-PSMA-R2 PET Imaging

The number and location of lesions identified by ⁶⁸Ga-PSMA-R2 PET imaging will be summarized and compared with those identified with conventional imaging techniques. Tumor uptake will be evaluated by SUV. SUV_{mean} and SUV_{max} will be determined along with tumor to background ratio and these will be summarized descriptively. Positive and negative lesions by the two imaging techniques will be cross tabulated overall and by localization area on a lesion level and a patient level. Agreement calculations for ⁶⁸Ga-PSMA-R2 imaging relative to conventional techniques will be performed on a patient level and summarized descriptively. Tests of association may be performed where appropriate.

Preliminary explorations of ⁶⁸Ga-PSMA-R2 imaging results relative to cytology and/or histopathology findings from archival and/or recent biopsy specimens will be performed for patients with biopsy data available.

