15.2.2. LESIONS DETECTED BY PET SCAN AND/OR CONVENTIONAL SCAN, BY TBR

The number of positive lesions detected by PET scan, correlated or not with conventional scan, will be presented by TBR category.

15.2.3. BURDEN AND LOCATION OF TUMOR LESIONS DETECTED BY ⁶⁸Ga-PSMA-R2 IN COMPARISON WITH CONVENTIONAL IMAGING MODALITIES SUCH AS CT/MRI AND/OR BONE SCAN.

- The difference of number of lesions detected by ⁶⁸Ga-PSMA-R2 PET scan and by conventional scan modalities such as CT/MRI and/or bone scan, will be displayed by location. The number of lesions detected on the PET scan, correlated and not correlated with conventional scan lesions, will be presented. The number of lesions detected on the conventional scan, not correlated with lesions detected on the PET scan, will be presented.
- The difference in the number of positive patients detected by ⁶⁸Ga-PSMA-R2 PET and by conventional scan modalities such as CT/MRI and/or bone scan, will be displayed by location. The number of positive patients detected on the PET scan, with at least 1 lesion correlated, and at least 1 lesion not correlated with a lesion detected on the conventional scan, will be presented. The number of positive patients detected on the conventional scan, with no lesions correlated with any lesion detected on the PET scan, will be presented. Note: A positive patient has at least 1 lesion detected.

15.2.4. CALCULATION OF PATIENT LEVEL AGREEMENT OF ⁶⁸Ga-PSMA-R2 PET IMAGING WITH CONVENTIONAL IMAGING IN PROSTATE CANCER PATIENTS

The patient level agreement is commonly used to characterize the agreement of a new test with the non-reference standard. Here ⁶⁸Ga-PSMA-R2 PET scan is the new test and conventional scan is the non-reference Standard.

		Conventional Scan	
		+	-
⁶⁸ Ga-PSMA-R2 PET Scan	+	a	b
	-	c	d
Total		a+c	b+d

The patient-level positive percent agreement, negative percent agreement and overall percent agreement will be calculated based on the number of patients with at least one positive lesion detected by conventional scan and/or at least one positive lesion detected by PET scan.

Document: K:\AAA\Ga-PSMA-R2\VYA27826\ Biostatistics\Documentation\SAP\v2.0\Ga-PSMA-R2-SAP_v2.0
 Author:  Version Number: 2.0

Version Date: 29JUN2020

Template No.: CS_TP_BS016 Revision 5
 Effective Date: 01Apr2018

Reference: CS_WI_BS005

These percent agreements will be calculated as follows with their two-sided 95% score confidence intervals:

- Positive percent agreement: $a/(a+c) * 100$

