- Negative percent agreement: $d/(b+d) * 100$
- Overall percent agreement: $(a+d)/(a+b+c+d) * 100$

Where

- a is the number of patients with at least one positive lesion detected by conventional scan and at least one positive lesion detected by PET scan
- b is the number of patients with at least one positive lesion detected by PET scan that is not correlated with conventional scan
- c is the number of patients with at least one positive lesion detected by conventional scan that is not correlated with PET scan
- d is the number of patients with no lesions detected by conventional scan or PET scan

These 3 coefficients and their 95% Clopper Pearson Exact confidence intervals will be calculated using SAS PROC FREQ as follow:

```
PROC FREQ data=temp;
  tables resp/binomial (exact level='1');
RUN;
```

The lesion-level positive percent agreement and overall percent agreement will be calculated based on the number of lesions detected as positive by conventional scan and/or by PET scan.

These percent agreements will be calculated as follows with their two-sided 95% score confidence intervals:

- Positive percent agreement: $a/(a+c) * 100$
- Overall percent agreement: $(a)/(a+b+c) * 100$

Where

- a is the number of lesions detected as positive in both PET and conventional scan
- b is the number of lesions detected as positive in PET scan but not correlated with conventional scan
- c is the number of lesions detected as positive in conventional scan but not correlated with PET scan

These 2 coefficients and their 95% Clopper Pearson Exact confidence intervals will be calculated using SAS PROC FREQ as above.

Document: K:\AAA\Ga-PSMA-R2\VYA27826\Biostatistics\Documentation\SAP\v2.0\Ga-PSMA-R2-SAP_v2.0
 Author:  Version Number: 2.0

Version Date: 29JUN2020

Template No.: CS_TP_BS016 Revision 5
 Effective Date: 01Apr2018

Reference: CS_WI_BS005

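### Protocol 8.1 labels a PET detection rate as patient-level agreement, and the patient-level cells in SAP 15.2.4 overlap and conflict with their own denominator sentence

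*Protocol*

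**What the plan says.** Protocol 8.1 states that no formal sample size calculation was done. It then supports the precision of 30 patients with an example: "if patient level agreement of 83.3% if observed (for e.g. if 25 patients had lesions detected by" PET out of 30, the 95% interval is 66.4% to 92.7%.

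Protocol 8.2.3 describes agreement as a comparison: calculations for PET "imaging relative to conventional techniques will be performed on a patient level and summarized descriptively". SAP 15.2.4 takes the same view: "patient level agreement is commonly used to characterize the agreement of a new test with the non-reference standard", with PET as the new test and the conventional scan as the non-reference standard. It prints a 2x2 table of PET +/- by conventional +/-, and defines positive agreement (PPA) as a/(a+c), negative agreement (NPA) as d/(b+d) and overall agreement as (a+d)/(a+b+c+d).

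The written cells under that table are:

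- a: patients with a lesion on both scans. No lesion match is required.
- b: "b is the number of patients with at least one positive lesion detected by PET scan that is not correlated with conventional scan"
- c: "c is the number of patients with at least one positive lesion detected by conventional scan that is not correlated with PET scan"
- d: patients with no lesion on either scan.

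The sentence before the formulas bases the percentages on the "number of patients with at least one positive lesion detected by conventional scan and/or at least one positive lesion detected by PET scan". The percentages are to be "calculated as follows with their two-sided 95% score confidence intervals". After the cell definitions the SAP adds: "These 3 coefficients and their 95% Clopper Pearson Exact confidence intervals will be calculated using SAS PROC FREQ as follow". The code that follows requests the exact interval only.

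**The concern.** The example in 8.1 never mentions the conventional result, so it cannot be an agreement figure as that term is used in 8.2.3 and SAP 15.2.4. In biochemical recurrence the two quantities can move in opposite directions: a PET lesion in a conventional-negative patient raises the detection rate and lowers agreement. PPA and NPA also rest on subsets of the 30 patients, so an interval on 30 overstates their precision.

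In SAP 15.2.4 the table has mutually exclusive cells but the written definitions do not. Neither b nor c requires the other scan to be negative. A patient with one matched lesion and one extra PET lesion meets a and b. A patient with one matched lesion and one unmatched conventional lesion meets a and c. The SAP expects mixed patients, because 15.2.3 plans counts of PET-positive patients with correlated and with uncorrelated lesions.

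Per-patient agreement is a stated secondary objective and endpoint. As written, two programmers could follow the plan and publish different percentages and intervals from the same data.

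**Working it through.** **1. The 8.1 interval.** Inputs: x = 25, n = 30, two-sided 95%, z = 1.96. The score interval is [p + z²/2n ± z·√(p(1−p)/n + z²/4n²)] / (1 + z²/n). With p = 25/30 = 0.833 it gives 66.4% to 92.7%, which is the stated figure. Clopper-Pearson gives 65.3% to 94.4%, so 8.1 used the score method and its arithmetic is right.

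**2. What 25 PET-positive patients imply for agreement.** Let K be the number of conventional-positive patients among 30, with exclusive cells. Then b = 25 − a, c = K − a and d = 30 − a − b − c = 5 − K + a, so a + d = 2a + 5 − K. Since d ≥ 0 and c ≥ 0, a runs from K − 5 to K (for K between 5 and 25).

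| K | a + d | Overall agreement |
|---|---|---|
| 10 | 5 to 15 | 16.7% to 50.0% |
| 12 | 7 to 17 | 23.3% to 56.7% |
| 15 | 10 to 20 | 33.3% to 66.7% |
| 18 | 13 to 23 | 43.3% to 76.7% |
| 20 | 15 to 25 | 50.0% to 83.3% |

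Reaching 25/30 needs a = (20 + K)/2 ≤ K, hence K ≥ 20. The planned mix is about 6 + 12 = 18 patients in biochemical recurrence and 12 metastatic (Protocol Synopsis), so K = 12 if the conventional reads follow eligibility.

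**3. Precision at 83.3% on the actual denominators (score method).**

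| Count | 95% CI | Width |
|---|---|---|
| 25/30 | 66.4% to 92.7% | 26 points |
| 15/18 | 60.8% to 94.2% | 33 points |
| 10/12 | 55.2% to 95.3% | 40 points |

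**4. Overlapping cells.** The counts are illustrative: all 12 metastatic patients have a matched lesion, 13 of the 18 in biochemical recurrence are PET-positive, and 5 patients are negative on both scans. In the second row, 6 of the 12 also have an extra PET lesion. In the third, 4 of the 12 also have an unmatched conventional lesion.

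| Reading | a, b, c, d | Sum | PPA | NPA | Overall |
|---|---|---|---|---|---|
| Exclusive cells | 12, 13, 0, 5 | 30 | 12/12 = 100% | 5/18 = 27.8% | 17/30 = 56.7% |
| Literal, 6 extra PET | 12, 19, 0, 5 | 36 | 12/12 = 100% | 5/24 = 20.8% | 17/36 = 47.2% |
| Literal, plus 4 unmatched conventional | 12, 19, 4, 5 | 40 | 12/16 = 75.0% | 5/24 = 20.8% | 17/40 = 42.5% |

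Overlap only enlarges b and c, so it can lower the three percentages but never raise them.

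**5. The denominator sentence.** Restricting to patients positive on at least one scan sets d = 0. With the exclusive cells above, NPA becomes 0/13 = 0% (it is always 0/b) and overall agreement 12/25 = 48.0%, against 27.8% and 56.7% with d included. The lesion-level block of the same section uses a parallel sentence, and there it fits, because that block has no d and no NPA.

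**The case against.** The 8.1 text is a hypothetical about interval width. The interval is correct for any 25/30, and no sample size rests on it. This stands, and it limits that part to a mislabelled example.

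The printed 2x2 table is already exclusive. If the PROC FREQ dataset holds one record per patient, totals of 36 or 40 cannot arise, and the output templates, which are not in the public documents, may settle the matter. But the SAP does not state the dataset structure, and neither point repairs definitions that contradict the table above them.

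The denominator sentence can be read loosely, as naming the positives from which the cells are built, because the formulas plainly include d. That is probably what was meant; the 0% result follows only from the literal reading.

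The 12/18 split is an assumption. Criterion 3b names no modality. Criterion 3a accepts CT/MRI or bone scan, and its imaging clause can be read as applying only after radiation therapy. Protocol 6.5.2 specifies central reading for comparison with PET only for Phase 2 metastatic patients, whereas SAP 15 uses vendor results from both phases. Which conventional reads enter for biochemical recurrence is therefore not settled. This is why other values of K are tabulated.

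The two interval methods could both be intended for reporting, and choosing between them is partly preference. SAP 6.1 already presents data by population and 15.2.3 already counts PET-positive patients, so the detection rate in biochemical recurrence is nearly available; only its interval is new.

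**Conclusion.** The concern holds. Protocol 8.1 attaches a correct interval to the wrong quantity: 25/30 is a PET detection rate. Under the planned 12/18 split, and if conventional reads follow eligibility, the same 25 patients correspond to overall agreement of 23.3% to 56.7%. No split with fewer than 20 conventional-positive patients reaches 83.3%.

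The overlap in SAP 15.2.4 follows from the text and needs no assumption. Its size depends on how many patients have both matched and unmatched lesions; in the examples it moves overall agreement from 56.7% to 47.2% or 42.5%, and PPA from 100% to 75.0%. The denominator sentence and the two interval methods are smaller ambiguities in the same section.

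The results are descriptive and no decision rule or sample size depends on them. This should be corrected, but it does not threaten the trial.

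**What to change.** **Protocol 8.1.** Call 25/30 = 83.3% (score 95% CI 66.4% to 92.7%) a PET detection rate, then add:

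> If about 12 patients are conventional-positive, a PPA of 10/12 = 83.3% has 95% CI 55.2% to 95.3%. If about 18 are conventional-negative, a PET detection rate of 15/18 = 83.3% has 95% CI 60.8% to 94.2%, which corresponds to an NPA of 3/18 = 16.7% (5.8% to 39.2%). With these counts overall agreement is 13/30 = 43.3% (27.4% to 60.8%).

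The text is self-consistent: 10 + 15 = 25 PET-positive, a = 10, b = 15, c = 2, d = 3, and (10 + 3)/30 = 43.3%.

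**SAP 15.2.4.**

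- Define exclusive patient-level cells: a, lesion on both scans; b, PET lesion and no conventional lesion; c, conventional lesion and no PET lesion; d, neither.
- Replace the denominator sentence with: the denominator is all patients with both scans read.
- Use lesion correlation only in the lesion-level table, and footnote how many cell-a patients have no matched lesion.
- Name one interval method. Score matches 8.1 and the SAP's first interval sentence. Make the PROC FREQ option agree.
- Report the PET detection rate in biochemical recurrence with its interval beside PPA and NPA. Note that overall agreement depends on the enrolment split and is lowered by PET-only findings in that group.

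**Cost.** Wording in two sections, one PROC FREQ option, one footnote and one extra proportion with its interval. The stated precision for PPA and NPA becomes less favourable, and the exact interval is no longer reported. No extra patients, scans or visits are needed.
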